7.3 Procedures for patient-participants

The following samples will be collected from all participants

- A combined nose and throat swab in viral transport media (x 2 as above)
- A finger-prick blood sample for immediate FebriDx testing (patients and clinical teams will be blinded to results as above)
- Venous blood sampling (EDTA, Serum and RNA Paxgene tubes, a total volume of not more than 16mls)

7.4 Withdrawal criteria

A patient-participant may decide to withdraw from the study at any time, without giving a reason, and with no detriment to their medical care or legal rights.

The CI/PI may withdraw a patient from the study in the interests of participant safety or the integrity of the research study, or on the advice of the Sponsor's representative (Research & Development (R&D) department).

Any patient who is withdrawing from the study has the options of withdrawing and having any data and/or samples collected so far retained or withdrawing and having their data and/or samples destroyed (although signed ICFs, minimal personal identifiable information to record the withdrawal, and any completed point-of-care test result will be retained). A note to file would normally be sufficient to record any withdrawal.

8 Safety

8.1 Investigator Responsibilities

The CI is responsible for the overall conduct of the study and compliance with the protocol and any protocol amendments. The CI/PI will be responsible for using medical judgement in assigning seriousness of SAEs and causality.

It is the responsibility of the CI/PI to ensure that all SAEs, as previously defined, are recorded and reported to the Sponsor within 24 hours of becoming aware of the event, and to provide further follow-up information as soon as it is available.

Responsibilities may be delegated to an appropriate member of the study site staff. Delegated tasks must be documented on a Delegation Log and signed by all those named on the list.

9 Statistics and data analysis

9.1 Sample size calculation

Assuming a sensitivity and specificity for the detection of bacterial infection (i.e. bacterial versus non-bacterial aetiology) of ~90%, for the combined HR-POCTs (33), a sample size of 200 samples containing 100 with bacterial (including bacterial/viral co-infection) and 100 patients with non-bacterial aetiology (i.e. viral and non-infected), using the reference standard of clinical adjudication, will allow an assessment of positive percentage agreement (sensitivity) and negative percentage agreement (specificity) with high precision (95%CIs of \pm 0) (39). In the PIs previous studies around 50% of all unselected patient with ARI have had bacterial infection as their adjudicated aetiology and therefore a sample of 200 patient should provide around 100 with bacterial infection. The samples size is based primarily on the performance of the bacterial component of the HR test as the principal intended use case of these tests is to guide antibiotic use.

9.2 Statistical analysis plan

Test results from the combined HR-POCTs will be compared to adjudicated aetiology using the different adjudication methods. Positive percentage agreement (PPA, used in place of sensitivity to reflect an imperfect reference standard), Negative percentage agreement (NPA, used in place of specificity to reflect an imperfect reference standard), positive predictive value (PPV), negative predictive value (NPV), and overall accuracy (with 95% confidence intervals), will be calculated for both bacterial (vs non-bacterial) and viral (vs non-viral) infection. ROC curves will be generated and AUC with 95%CI calculated. Performance metrics including AUROC will be compared between the tests using Chi Squared test and DeLong test.

10 Data management

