FebriDx (Lumos diagnostics, Carlsbad, US) is a point-of-care test (POCT) that detects 2 host immune response proteins, one raised with bacterial infection (CRP) and one raised in viral infection (Myxovirus resistance protein A) in a finger-pick blood sample. It is an instrument-free, immunochromatographic, lateral flow-based test with results in 10 minutes. The read-out is the presence or absence of 3 coloured lines assessed by visual inspection, with suggested interpretation provided by the manufacturer, figure 1a (19).

MeMed BV (MeMed, Tirat Carmel, Israel) detects 3 host immune response proteins; CRP, Interferon gammainduced protein 10 (raised in viral infection) and TNF-related apoptosis-inducing ligand (raised in viral and reduced in bacterial infection). The levels of these 3 proteins are computationally integrated into a score. The test uses an analyser (MedMed Key, a small-footprint immunoassay platform) that can be located at the point-of-care. Blood samples are loaded into a cartridge which is inserted into the analyser with results in 15 minutes. The read-out is a score from 0-100, divided into bands which indicate the likelihood of a bacterial or viral infection, based on pre-set cut-off values, figure 1b (20,21).

An alternative approach to detecting host immune response proteins testing is the detection of host mRNA (i.e. transcriptomic) to differentiate bacterial from viral infection. The TriVerity Acute Infection and Sepsis Test (Inflammatix, Sunnyvale, CA, USA), uses an isothermal reverse-transcribed loop-mediated amplification (qRT-LAMP) assay to measure levels of 29 host mRNAs in blood and incorporates machine learning to calculate 3 separate scores predicting the likelihood of bacterial infection, viral infection and illness severity. This 29 gene set classifier has shown good levels of accuracy at distinguishing bacterial and viral infection across a range of clinical infection syndromes. The test is not yet FDA approved or CE marked but this is expected early in 2025.

Why is this research important?

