7.1 Aims and objectives

To evaluate the diagnostic accuracy for the 2 commercially available combined HR-POCT platforms (MeMed BV and FebriDx) and for the Triverity test, for the diagnosis of bacterial and viral infection, against the reference standard of clinical adjudication.

Outcome measures

Key outcome measures:

Positive percentage agreement (PPA) negative percentage agreement (NPA), Positive Predictive Value (PPV), Negative Predictive Value (NPV), Overall accuracy, AUROC, all with 95% confidence intervals.

Exploratory outcome measures:

To evaluate the equivalence of EDTA blood and PAXgene RNA blood on gene expression values for the prototype Cepheid HR test (Xpert Bacterial vs. Viral assay).

Study design and methods

We will conduct a fully powered diagnostic accuracy study performed on samples prospectively collected from adults presenting with ARI (7) using the Southampton Research Biorepository (SRB) and including routinely collected clinical data including results of diagnostic testing for viruses and bacteria in addition to baseline clinical, laboratory and radiological data, and outcome data. The reference standard used by regulators for defining bacterial and viral infection is clinician adjudication (as no sufficiently accurate gold standard test exists) which take account of detailed clinical data including diagnostic tests for pathogens, blood test results (eg white cell count, PCT) radiological tests, and other data (37).

In accordance with guidelines, adjudication will be performed independently by three blinded experts, with a system for arbitration where there is discordance (37). Full methods for clinical adjudication are detailed in Tanner A, at al, Journal of Infection 2024 (38) Measures of diagnostic accuracy will be calculated for each HR test separately and compared.

Trial overview for patient-participants

Adult patients with acute respiratory illness in Southampton General Hospital's Emergency Department (ED) and Acute Medical unit (AMU) will be identified and assessed for eligibility for the trial. Potential participants would have been seen and assessed by the triage nurse or other triaging clinician but may not have been fully treated by their clinician. The triage nurse or other triage clinician may highlight potential participants to the study team. Potential participants will receive a participant information sheet, and be invited to ask questions, as part of the informed written consent process.

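### The between-test AUROC comparison in section 9.2 sets FebriDx, read as lines present or absent, against two scored tests, so a lower AUROC for FebriDx would not show lower accuracy at the cut-off

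*Protocol*

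**What the plan says.** The study evaluates accuracy "for the 2 commercially available combined HR-POCT platforms (MeMed BV and FebriDx) and for the Triverity test" (Protocol 7.1). AUROC is among the key outcomes in the summary table and again in 7.1: "Overall accuracy, AUROC, all with 95% confidence intervals". The design text under 7.1 adds: "Measures of diagnostic accuracy will be calculated for each HR test separately and compared". Section 9.2 then fixes the method: "ROC curves will be generated and AUC with 95%CI calculated", and "Performance metrics including AUROC will be compared between the tests using Chi Squared test and DeLong test".

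The Background (section 7) describes three different read-outs:

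- FebriDx: "The read-out is the presence or absence of 3 coloured lines assessed by visual inspection".
- MeMed BV: "The read-out is a score from 0-100, divided into bands", with bands set by pre-set cut-offs.
- TriVerity: it "incorporates machine learning to calculate 3 separate scores predicting the likelihood of bacterial infection", and likewise viral infection and severity.

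Nowhere is FebriDx excepted from the AUROC comparison, and no rule says how a line result is to be turned into an ROC curve.

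**The concern.** AUROC summarises how well a test ranks patients over all possible thresholds. For MeMed BV and TriVerity there is a score to rank by. For FebriDx, as described, the bacterial (or viral) result is a call, which gives one operating point joined to the corners by two straight segments. Comparing that area with the area under a full curve is not like for like. Two tests with the same PPA and NPA at their cut-offs would usually have different AUROCs.

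The stake is interpretation. Section 9.1 gives guiding antibiotic use as the main intended use, which depends on performance at a cut-off. The Background says independent evidence is needed because earlier studies were company-supported. A significant AUROC deficit for one product, on a key outcome, could easily be taken as worse classification when classification is equal.

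**Working it through.** **Plan's own figure.** The protocol gives no AUROC value, AUROC difference or power, so there is none to reproduce.

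**Inputs from the protocol.** Sensitivity and specificity about 90% for bacterial versus non-bacterial, and 100 patients in each class (9.1). Cited range of accuracy 85-95% (section 7, review of evidence).

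**Inputs assumed.** The shape of the score distributions and the within-class correlation (rho) between tests. The protocol gives neither.

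**Step 1: AUC at the same operating point.**

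- Two-category test: AUC = (PPA + NPA)/2.
- Equal-variance binormal score through the same point: AUC = Φ(d/√2), with d = z(PPA) + z(NPA).
- At 90/90: (0.90 + 0.90)/2 = 0.900. d = 2 × 1.2816 = 2.563, so Φ(2.563/1.414) = Φ(1.812) = 0.965.

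| PPA = NPA | Positive/negative call | Binormal score | Gap |
|---|---|---|---|
| 85% | 0.850 | 0.929 | 0.079 |
| 90% | 0.900 | 0.965 | 0.065 |
| 95% | 0.950 | 0.990 | 0.040 |

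**Step 2: sensitivity to the equal-variance assumption.** For a binormal curve through 90/90 with SD ratio b, AUC = Φ(1.2816(1+b)/√(1+b²)), which is largest at b = 1.

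- b = 0.5: Φ(1.922/1.118) = Φ(1.719) = 0.957.
- b = 0.3: Φ(1.666/1.044) = Φ(1.596) = 0.945.

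So 0.065 is the top of this family. At b = 0.3 the gap is 0.945 − 0.900 = 0.045.

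**Step 3: what DeLong would report.** Paired DeLong, two-sided 5%, 100 v 100 patients, one test as a score and the other as a thresholded call with the same d. There were 2,000 runs per row. The score test had the higher AUC in every significant result.

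| PPA = NPA | rho 0 | rho 0.5 | rho 0.8 |
|---|---|---|---|
| 85% | 71% | 89% | 98% |
| 90% | 80% | 91% | 99% |
| 95% | 76% | 83% | 93% |

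A separate set of 1,500 runs at 90/90 gave 79% at rho 0 and 96% at rho 0.7, hence roughly 79-99% overall at 90/90.

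**Step 4: like for like.** With both tests reduced to positive/negative calls at 90/90, the true AUC difference is 0 and DeLong rejects in 5.0%, 5.1% and 5.8% of runs (rho 0, 0.5, 0.8). The result in step 3 therefore comes from the difference in read-out.

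**Step 5: FebriDx coded as three ordered categories.** A second cut is added below the first, at 0 or 0.6 on the non-bacterial scale (assumed). With the cut at 0, the ROC points are (0, 0), (0.10, 0.90), (0.50, 0.995) and (1, 1). The area is 0.045 + 0.379 + 0.499 = 0.923. With the cut at 0.6 it is 0.925. Against 0.965 the gap is about 0.04. DeLong finds FebriDx lower in 45-52% (rho 0), 59-66% (rho 0.5) and 79-87% (rho 0.8) of 1,000 runs each.

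**The case against.** Several points on the other side are sound.

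- **The larger area is not a law.** A monotone ROC curve through (0.10, 0.90) can have any area from 0.90 × 0.90 = 0.81 to 0.10 × 0.90 + 0.90 × 1 = 0.99. The score test has the larger area only if its curve lies above the two straight segments, as a concave curve does.
- **DeLong is not invalid here.** It handles ties. A reader might infer that the 79-99% are false positives. They are not: the population AUCs differ, and the percentages are power to detect that difference. A score that ranks patients within the positive and negative groups carries real information that a line reading discards.
- **The coding of FebriDx is unknown.** The Background refers to a manufacturer's interpretation in a figure that is not reproduced in the text available. A graded coding narrows the gap (step 5).
- **Other measures give the right picture.** AUROC is one of six key measures, and the other five are untouched. The protocol has no ranking rule, superiority hypothesis or AUROC threshold. A reader might infer that this comparison would decide an overall ranking of the products; nothing in the text supports that.
- **Coding and choice of pairs could be left to a separate SAP.** That is true of details. But 9.2 already names the metric, the test and a comparison between the tests, with no exception. An analysis plan that followed it would carry over the same comparison.

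These points limit the size and wording of the concern. They do not make the comparison like for like.

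**Conclusion.** The point holds in a bounded form. As written, 9.2 compares AUROC between a test described as lines present or absent and two tests described as scores. At equal 90/90 accuracy the AUCs would be 0.900 and 0.965 under an equal-variance binormal score, or 0.945-0.957 for the score at SD ratios of 0.3-0.5. With 100 v 100 patients DeLong would find FebriDx lower in roughly 79-99% of studies, or roughly 45-87% with three ordered categories. The rejection rates were simulated for the equal-variance case only and would be expected to fall somewhat with the smaller gaps.

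The direction rests on the score tests having ROC curves above the two segments. The size rests on assumed distributions and correlations that the protocol does not give. The AUC difference is genuine but reflects granularity of the read-out, not accuracy at the cut-off. It would be wrong to conclude that FebriDx must look inferior whatever the data, or that the other accuracy measures are distorted.

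**What to change.** In the summary table, 7.1 and 9.2:

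- Limit the between-test AUROC/DeLong comparison to MeMed BV against TriVerity.
- Compare FebriDx with each of them on PPA and NPA by a paired method, since all three tests are run on the same patients. Use for each score test a cut-off fixed before analysis. The protocol documents pre-set cut-offs for MeMed BV only, so TriVerity's must be stated.
- If one figure is wanted, plot FebriDx as a single point on the ROC plot of the other two.

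The cost is a wording change, with no new patients, samples or data. The downside is that FebriDx has no between-test AUROC comparison.

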Once SRB generic consent has been obtained participants will be asked for 2 combined nose and throat swabs (1 sent for immediate respiratory viruses testing and the other to be stored at -80°C), finger-prick capillary blood sampling (for immediate FebriDx testing) and venous blood sampling (for ETDA, serum and RNA PAXgene tubes). Results of the FebriDx test will not be shared with treating clinicians or patients. The other tests will be performed retrospectively on stored samples at least 30 days later and will not influence clinic care.

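### Section 9.2 compares proportion metrics between tests run on the same patients with a Chi-squared test, which ignores the pairing and probably costs power

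*Protocol*

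**What the plan says.** Section 7.1 of the protocol (study design and methods) plans a between-test comparison: "Measures of diagnostic accuracy will be calculated for each HR test separately and compared". Section 9.2 names the methods: "Performance metrics including AUROC will be compared between the tests using Chi Squared test and DeLong test". No paired method for proportions is named anywhere in the document.

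The sampling is within patients. Section 7.3 lists swabs, finger-prick blood and venous blood under "The following samples will be collected from all participants". Section 7.1 (trial overview) says what the blood is for: "finger-prick capillary blood sampling (for immediate FebriDx testing" on the spot, and venous tubes for the rest, where "The other tests will be performed retrospectively on stored samples at least 30 days later". The natural reading is that each patient contributes a result on FebriDx, MeMed BV and TriVerity, each set against one adjudicated aetiology.

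The sample size in Section 9.1 rests on "Assuming a sensitivity and specificity for the detection of bacterial infection (i.e. bacterial versus non-bacterial aetiology) of ~90" per cent, and on "a sample size of 200 samples containing 100 with bacterial (including bacterial/viral co-infection) and 100 patients with non-bacterial aetiology".

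**The concern.** A Pearson Chi-squared test of 90/100 against 80/100 treats the figures as coming from 200 different people. Here they come from the same 100 bacterial patients, each tested twice. The information about a difference lies in the discordant patients, those whom one test classifies correctly and the other does not. Pearson's test never looks at them.

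PPV and NPV have a further difficulty. Their denominators are the test-positives and test-negatives, which differ between tests and overlap in patients, so independence fails there too.

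Comparison is the first word of the study title. If the tests tend to be right and wrong on the same patients, the unpaired test discards the main statistical advantage of the design. A real gap in PPA may then be reported as not significant and misread as similar performance. Section 7 stresses the risk of undertreating bacterial infection, so that misreading would matter.

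**Working it through.** **Inputs from the protocol.** PPA and NPA of about 90%, and 200 patients with about half bacterial (Section 9.1). Check: 200 × 0.50 = 100 bacterial and 100 non-bacterial, as stated.

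**Inputs assumed.** The protocol gives no within-patient correlation, no alpha for between-test contrasts and no difference of interest. I take phi from 0 to 0.5, two-sided 5%, and a comparator PPA of 80%.

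**1. One worked result.** Test A detects 90/100 and test B 80/100 of the same bacterial patients.

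- Pearson: the pooled proportion is 0.85, so X² = 0.10² / (2 × 0.85 × 0.15 / 100) = 0.01 / 0.00255 = 3.92, p = 0.048, however the patients pair.
- McNemar: X² = (b − c)² / (b + c), where b and c are the discordant counts.

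| b / c | phi | McNemar X² | p |
|---|---|---|---|
| 18 / 8 | 0 | 100/26 = 3.85 | 0.050 |
| 14 / 4 | 0.33 | 100/18 = 5.56 | 0.018 |
| 12 / 2 | 0.50 | 100/14 = 7.14 | 0.008 |

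For the last row, 78 patients are positive on both tests and 8 negative on both, so phi = (78 × 8 − 12 × 2) / √(90 × 10 × 80 × 20) = 600/1200 = 0.50.

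**2. Why the direction is conservative.** The variance of the difference is [p₁(1−p₁) + p₂(1−p₂) − 2·phi·√(p₁(1−p₁)p₂(1−p₂))] / n. The unpaired test drops the last term. At 90% v 80% and n = 100:

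- unpaired: (0.09 + 0.16)/100 = 0.0025, standard error 5.0 points;
- paired, phi 0.5: (0.25 − 0.12)/100 = 0.0013, standard error 3.6 points.

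With positive phi the unpaired standard error is too large.

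**3. Error rate and power.** Simulation of paired binary results, n = 100, 200,000 runs per setting. Type I error at 90% v 90%:

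| phi | Chi-squared | McNemar, asymptotic |
|---|---|---|
| 0 | 5.1% | 5.0% |
| 0.3 | 2.1% | 4.4% |
| 0.5 | 0.7% | 4.4% |

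Power at 90% v 80%:

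| phi | Chi-squared | McNemar, asymptotic | McNemar, mid-p | McNemar, exact |
|---|---|---|---|---|
| 0 | 52% | 52% | 49% | 42–43% |
| 0.2 | 52% | 61% | 59% | 52% |
| 0.3 | 52% | 67% | 65% | 58% |
| 0.5 | 52% | 81% | 81% | 73% |

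By symmetry the same figures apply to NPA in 100 non-bacterial patients.

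**4. All three tests at once.** With every PPA at 90%, a Pearson test on 2 degrees of freedom has type I error 5.1% with no correlation, 2.8% at phi about 0.2 and 0.8% at about 0.4. Cochran's Q stays at about 5%.

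**5. What pairing does not touch.** A single test's interval uses only that test's results. At 90/100 the half-width is 1.96 × √(0.9 × 0.1/100) = 5.9 points whether or not other tests were run on the same patients.

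**The case against.** Several points on the other side are fair.

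- **The term is loose.** McNemar's statistic is itself referred to a chi-squared distribution, and choosing DeLong shows that a method suited to correlated curves was picked for AUROC. The authors may have meant a paired test, and a separate analysis plan could say so. This softens the point, but 9.2 names a test whose ordinary meaning is Pearson's, and an analyst following it would run that.
- **The correlation is unknown.** At phi 0 the Chi-squared and asymptotic McNemar tests agree. The document-based reason to expect positive phi is that FebriDx and MeMed BV both measure CRP (Section 7). That covers one of the three pairs, since TriVerity measures host mRNAs. This stands as a limit on size.
- **The key objective is elsewhere.** It is each test's accuracy against adjudication, and the sample size is built on single-test precision. Neither is affected, so this point should be fixed but does not undermine the study.

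A reader might infer more than the documents support:

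- **That the planned confidence intervals are wrong.** Section 9.2 plans intervals only for each test's own metrics and AUC, and pairing does not affect these. No interval for a between-test difference is specified.
- **That false claims of superiority will multiply.** With positive correlation the PPA and NPA error goes the other way.
- **That every comparison is affected.** DeLong handles correlated AUROCs.
- **That any form of McNemar recovers the full power.** The exact version gives 58% and 73% at phi 0.3 and 0.5, and is below Chi-squared at phi 0.

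**Conclusion.** The point holds for the between-test p-values of PPA, NPA, PPV, NPV and accuracy. The test named in 9.2, in its ordinary form, does not fit a design in which the same patients take all three tests. If results correlate positively within patients, the PPA and NPA comparisons are conservative: a nominal 5% test runs at 2.1% (phi 0.3) or 0.7% (phi 0.5). Power to detect 90% against 80% stays near 52%, where asymptotic or mid-p McNemar would give 65–67% or about 81%.

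These sizes rest on assumed values of phi, a two-sided 5% level and an 80% comparator. For PPV and NPV the independence assumption also fails, but neither the size nor the direction of the effect was calculated, so none is claimed. This should be fixed before the comparisons are run.

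**What to change.** In Section 9.2, replace the Chi-squared test with:

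- **PPA, NPA and overall accuracy:** McNemar's test, asymptotic or mid-p, optionally after Cochran's Q across the three tests, with a paired 95% confidence interval for each difference. Use reference-positive patients for PPA, reference-negative patients for NPA and all patients for accuracy. Each pairwise comparison uses patients with valid results on both tests.
- **PPV and NPV:** a method for correlated predictive values, such as a generalised score test, GEE or a patient-level bootstrap. McNemar does not fit their differing denominators.
- **AUROC:** keep DeLong.

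The cost is a sentence or two of text. No new data, samples or patients are needed.
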